11.2 Subject Confidentiality	27
11.3 Study Modification/Discontinuation	27
12. ETHICAL CONSIDERATIONS.....	28
12.1 Risk/Benefit Assessment.....	28
12.2 Pediatric Populations.....	28
13. PUBLICATION OF RESEARCH FINDINGS	28
14. REFERENCES	29

SYNOPSIS

Study Title

Compatibility of triheptanoin (C7) with the Ketogenic Diet in Patients Diagnosed with Glucose Transporter Type 1 Deficiency (G1D)

Objectives

Primary Objectives: To explore triheptanoin (C7 oil; C7) compatibility with the ketogenic diet by evaluating EEG (for the determination of outcome EEG as defined below), and seizure rate, glycemia and ketosis in proven G1D patients receiving (both prior to enrolment and for the duration of this study) a ketogenic diet.

Secondary Objectives: N/A

Design and Outcomes

This is a single-site, open-label proof of principle exploratory trial to investigate the compatibility of C7 oil with the ketogenic diet in subjects genetically diagnosed with G1D. The primary outcome measure is change in EEG during C7 supplementation. The secondary outcome measures are: changes in seizure rate, glycemia (blood glucose levels), and ketosis (beta-hydroxybutyrate levels).

Interventions and Duration

This is an open-label, single arm proof of principle trial of orally-administered C7 in subjects diagnosed with G1D and currently receiving (i.e., prior to enrolment) a ketogenic diet. The ketogenic diet will have been previously prescribed by the patient's treating physician independently of this study and for clinical reasons (i.e., the treatment of G1D epilepsy). **Because the ketogenic diet supplies well over 50% of calories from fat, subjects, who are already tolerating over this much fat as part of their previously-prescribed ketogenic diet, will replace 45% of their daily caloric intake with C7** for 24 hours, during a 48 hour inpatient stay. During observation, subjects will have continuous EEG to monitor for any potential C7-related changes in seizure activity before, during, and after C7 ingestion. Subjects will undergo clinical evaluation and comprehensive blood work at baseline and discharge, and continuous EEG and evaluation of glucose and beta-hydroxybutyrate levels while inpatient and receiving C7. Total time of participation is 4 days.

Sample Size and Population

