9. STATISTICAL CONSIDERATIONS

9.1. General Design Issues

The main aim of this proof of principle trial is to evaluate the compatibility of C7 with ketogenic diet in subjects diagnosed with G1D. This protocol will yield data that allow a go/no-go decision regarding whether C7 should proceed to an efficacy trial:

If EEG, clinical seizure activity, glycemia and ketosis (blood beta-hydroxybutyrate level) under the ketogenic diet remain unaltered (i.e., unchanged from normal laboratory value ranges) in at least 3 out of 5 G1D subjects in each age group after the partial substitution of ketogenic diet fat with C7, we will confirm compatibility of C7 with ketogenic diet and recommend proceeding to an efficacy trial for C7.

The sample size estimation for this optimal two-stage design is given in Section 9.3.

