9.3. Sample Size and Accrual

In this exploratory pilot study, we will recruit 5 subjects in each of three age groups for a total of 15 subjects. The sample size is not justified because this is an exploratory pilot study that will yield data aimed to enable important future combined or comparative studies. We expect to complete the enrollment of study within 24 months.

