9.5. Data Analyses

Descriptive statistics will be computed for each group and combined age group in this pilot exploratory study. For normally distributed, continuous data, means and standard deviations will be used to describe the demographic and clinical characteristics of the patient population participating in the study. Medians, quartiles, and ranges will be used to describe characteristics of the patient population when the data are continuous, non-normally distributed. For categorical or dichotomous variables, the frequency or the proportion will be reported. The proportion of patients who do not alter EEG in subjects currently receiving the ketogenic diet will be computed along with the corresponding 95% confidence interval using the exact binomial method. The proportion of patients who have stable blood glucose and beta hydroxybutyrate levels during acute and long-term C7 supplementation will be computed using exact binomial method.

Paired t-tests or nonparametric one-sample signed tests will be conducted to test if there were significant changes in EEG and neurological performance indices such as ataxia in G1D patients receiving a normal diet between pre-C7 and post-C7. The objective of this study is to enable future combined or comparative studies to evaluate C7 comparability with the ketogenic diet by evaluating EEG and preservation of glycemia and ketosis. Descriptive statistics will be computed to inform (but not to determine; per the FOA) the sample size needed for a future larger study.

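### Section 9.1 says a 3-of-5-per-group result will confirm compatibility, but this unsized single-arm pilot can only give preliminary support: the rule can be met with up to 6 of 15 subjects altered after C7

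*Combined protocol and SAP*

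**What the plan says.** Section 9.1 sets a go/no-go rule. EEG, clinical seizure activity, glycemia and ketosis must remain unaltered "in at least 3 out of 5 G1D subjects in each age group" after part of the dietary fat is replaced by C7. If so, "we will confirm compatibility of C7 with ketogenic diet and recommend proceeding to an efficacy trial for C7". That sentence does two things: it recommends a next step, and it states a conclusion.

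The rest of the plan is more modest. The Synopsis states: "This is a single-site, open-label proof of principle exploratory trial". Section 9.3 says "we will recruit 5 subjects in each of three age groups for a total of 15 subjects" and adds: "The sample size is not justified because this is an exploratory pilot study". Section 9.1 also states: "The sample size estimation for this optimal two-stage design is given in Section 9.3". The text of 9.3 gives no stages, bounds, null rate, target rate or error rates.

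Section 9.5 plans descriptive statistics for each age group and for the groups combined. The proportion with unaltered EEG is to be "computed along with the corresponding 95% confidence interval using the exact binomial method". The exact binomial method is also named for stable glucose and beta-hydroxybutyrate. None of these intervals is tied to the decision in 9.1.

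**The concern.** The hypotheses in 1.1 and 9.2 are of no interference: no EEG change, no rise in observable seizures, and no clinically relevant change in glucose or ketones. The rule would declare this confirmed although up to two subjects in every group had changed. No unacceptable rate, target rate or required lower confidence bound is attached to it, and its chance of returning a go is not given.

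Someone who reads of a go would take it that compatibility with the ketogenic diet had been shown. Section 2.1 says the result is meant to enable later combined or comparative studies, so the claim would be carried forward. An alteration may not be trivial: section 7 itself raises the possibility that C7 takes a subject out of ketosis quickly, with breakthrough seizures. The exposure is one day (5.1.1), a limit that the 9.1 conclusion does not carry.

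**Working it through.** **Plan's own figure.** The total of 15 is 3 groups × 5 subjects. There is no power or precision calculation to reproduce, because 9.3 says the size is not justified.

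**Inputs.** Threshold of 3 of 5 in each of three groups (9.1); 5 per group, 15 in all (9.3); exact binomial 95% interval (9.5), taken as two-sided Clopper-Pearson. Assumptions: one composite call per subject (unaltered only if all four measures are), independent subjects, the same true unaltered rate p in each group, and all 15 evaluable. The values of p are assumed and shown as a range.

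**Step 1: the least favourable result that passes.** 3 + 3 + 3 = 9 of 15 unaltered (60%), so 15 − 9 = 6 altered (40%). This passes only if the six are split 2/2/2.

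**Step 2: precision.** For x unaltered of n, the lower limit is the 0.025 quantile of Beta(x, n − x + 1), and the upper limit is the 0.975 quantile of Beta(x + 1, n − x).

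| Result | Exact 95% interval for the unaltered proportion |
|---|---|
| 3/5 (one group, minimum pass) | 14.7% to 94.7% |
| 5/5 (one group, best case) | 47.8% to 100% |
| 9/15 (pooled, minimum pass) | 32.3% to 83.7% |
| 15/15 (pooled, best case) | 78.2% to 100% |

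At 9/15 the interval includes unaltered rates below 50%, so the data would not exclude that most patients are altered. At 15/15 it still leaves room for up to 100 − 78.2 = 21.8% altered.

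**Step 3: chance of a go.** P(go) = [P(Bin(5, p) ≥ 3)]³.

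| True unaltered rate p | One group passes | P(go), all three pass |
|---|---|---|
| 32% | 0.1905 | 0.7% |
| 40% | 0.3174 | 3.2% |
| 50% | 0.5000 | 12.5% |
| 60% | 0.6826 | 31.8% |
| 70% | 0.8369 | 58.6% |
| 80% | 0.9421 | 83.6% |
| 90% | 0.9914 | 97.4% |

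For example, at 60%: 0.6826³ = 0.318. So if 40% of patients are truly altered after C7, the plan would state that compatibility is confirmed about one time in three.

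**Step 4: the other way of counting.** If the rule were applied to each measure separately, two of five subjects could be altered on each of four measures. That is 2 × 4 = 8 alterations among 5 subjects, so every subject could be altered on something and the group still pass. The 6/15 and 9/15 figures belong to the composite reading only.

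**The case against.** The strongest reply is that this is a pilot in a rare disease. A lenient gate is legitimate there, 9.3 is open about the unjustified size, and 9.5 says the results will inform, not determine, the size of a later study. All of that stands, and it supports keeping the threshold. It does not support the word 'confirm'; pilot status is the reason to avoid it.

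Several stronger readings are tempting and should be set aside.

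- *Any result with 6 of 15 altered passes.* It does not. If six altered subjects fell at random among the 15, a 2/2/2 split would occur in C(5,2)³ / C(15,6) = 1000/5005 = 20% of allocations. Even 12 of 15 unaltered fails if the three altered subjects share a group.
- *C7 destabilised 40% of subjects.* With one arm, the most that can be said is altered after C7. The word 'unaltered' in 9.1 also has no direction, so an improved EEG might count as altered.
- *The 32% limit shows that a false go is likely.* It shows imprecision at the boundary result. At a true rate of 32%, all three groups would pass only about 0.7% of the time.
- *The plan reports no intervals.* Section 9.5 already has an exact interval for EEG and reporting by group and combined. What is missing is an interval for the go criterion itself, placed beside the decision.

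It is also fair to say that the 9/15 interval is constructed here. The plan specifies an exact 95% interval for the EEG proportion, not for a four-measure composite, and the text does not say that a composite is intended.

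**Conclusion.** The concern holds for the conclusion attached to the rule, not for the threshold or for making a go/no-go recommendation. An exploratory, unsized, single-arm study of 15 subjects cannot confirm the no-change hypotheses of 1.1, and the 9.1 wording should be changed.

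The size rests on the assumptions listed above. The composite call is the one that matters most, because the text leaves it open and the 6-of-15 count and pooled interval depend on it. The mismatch between 'confirm' and a design without stated error rates does not depend on it. The go probabilities would also shift if rates differed between age groups or if subjects were not evaluable, which the rule does not address.

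**What to change.** 1. In 9.1, replace "we will confirm compatibility of C7 with ketogenic diet and recommend proceeding to an efficacy trial for C7" with neutral text, for example: *the pre-specified go criterion will be considered met; this is preliminary support, limited to one day of exposure, for proceeding to an efficacy trial.* Wording such as 'no signal of incompatibility' should be avoided, because up to 6 of 15 subjects could be altered when it is used.
2. In 9.5, extend the EEG interval to the go criterion. Report the pooled (n = 15) and per-group unaltered proportions with exact 95% intervals, and the number of altered subjects, beside the go/no-go statement.
3. In 9.3, state the go probabilities at true unaltered rates of 50% to 90%, with their assumptions: one call per subject, independence, and a common rate.
4. Leave the 3-of-5 threshold unchanged.

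The cost is a less favourable stated conclusion and a little more reporting. No extra subjects or procedures are needed.

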9.2. Outcomes

9.2.1. Primary outcome

9.2.1.1. EEG

C7 metabolism will not interfere with previously-acquired ketosis in G1D, as measured by no change in EEG from pre-C7 baseline.

Subjects receiving C7 supplementation will experience no interference with ketosis, as measured by no change in EEG.

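### The primary outcome of no change in EEG has no variable, window, threshold or specified reading procedure, so the call that feeds the go/no-go rule can be settled after the recordings are seen

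*Combined protocol and SAP*

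**What the plan says.** The synopsis names the endpoint: "The primary outcome measure is change in EEG during C7 supplementation". Its objectives say that EEG is evaluated "for the determination of outcome EEG as defined below". The hypotheses in section 1.1 and the outcome text in 9.2.1.1 then restate the endpoint ("as measured by no change in EEG from pre-C7 baseline") without saying what is measured. Section 9.2.1.1 adds only: "Subjects receiving C7 supplementation will experience no interference with ketosis, as measured by no change in EEG".

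Other sections that touch the EEG outcome:

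- **Section 3** places the EEG evaluation at assessments before and after C7, whereas the synopsis speaks of change during supplementation.
- **Section 6.3.9** describes the electrode cap and about 48 hours of recording. It gives no scoring method and no reader.
- **Section 9.1** requires EEG, clinical seizures, glycemia and ketosis all to be unaltered in three or more of the five subjects in every age group. It explains unaltered by laboratory normal ranges.
- **Section 9.2.1.2** gives glucose and beta-hydroxybutyrate a tolerance, typically 2 SD. EEG has no counterpart.
- **Section 9.5** uses EEG in two ways. One is a yes/no classification: "The proportion of patients who do not alter EEG in subjects currently receiving the ketogenic diet will be computed". The other is a paired comparison: "Paired t-tests or nonparametric one-sample signed tests will be conducted to test if there were significant changes in EEG". It names no EEG variable for either, and the paired-test sentence goes on to refer to patients on a normal diet.

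On design, the synopsis says: "This is an open-label, single arm proof of principle trial". No section says who reads the EEG for the outcome, or whether that person knows which segments fall after the start of C7.

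**The concern.** Two long recordings from one person always differ in some respect, so no change has meaning only against a stated variable and tolerance. Without them, someone must decide which feature to look at, in which hours, and how much difference to allow. Nothing in the plan stops those choices from being made with the recordings in view.

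This matters because the EEG call has a consequence. Under 9.1 it helps decide whether compatibility is declared confirmed and an efficacy trial recommended. No change is both the hypothesis and the result that produces a go. Treatment is open and there is no control arm, so an undefined reading has no other safeguard.

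**Working it through.** **1. The plan's own figure.** 3 age groups × 5 subjects = 15, which agrees with section 9.3. That section gives no alpha, power or reference rate and says that the size is not justified, so there is no further calculation to reproduce.

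**2. Can the go rule be applied to EEG as written?** The only explanation of unaltered in 9.1 is laboratory normal ranges. The 2 SD tolerance in 9.2.1.2 covers glucose and beta-hydroxybutyrate only. Neither classifies an EEG, so the EEG part of the rule cannot be applied without a definition from outside the plan.

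**3. How much could a lenient call matter?** This is an illustration, because the documents give no rates.

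Input from the plan (9.1): at least 3 of 5 in each of three groups.

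Assumptions:
- The true share unaltered on all components is 0.40. This is below the 3/5 = 0.60 that the rule asks for, so a go is called false here.
- m is the share of changed EEGs called unchanged: 0.1, 0.2 or 0.3.
- s is the share of altered subjects who fail on EEG alone. A lenient EEG call cannot rescue anyone who also fails on seizures, glucose or beta-hydroxybutyrate.
- Subjects and age groups are independent, with the same rate in each group.

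Formulas:
- Share called unaltered: q = 0.40 + 0.60 × s × m
- One group passes: G(q) = 10q³(1−q)² + 5q⁴(1−q) + q⁵
- All three pass: P(go) = G(q)³

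With m = 0: G(0.40) = 0.2304 + 0.0768 + 0.0102 = 0.3174, and 0.3174³ = 3.2%.

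| s | m | q | G(q) | P(go) |
|---|---|---|---|---|
| 1 | 0.1 | 0.46 | 0.4253 | 7.7% |
| 1 | 0.2 | 0.52 | 0.5375 | 15.5% |
| 1 | 0.3 | 0.58 | 0.6475 | 27.1% |
| 0.5 | 0.1 | 0.43 | 0.3705 | 5.1% |
| 0.5 | 0.2 | 0.46 | 0.4253 | 7.7% |
| 0.5 | 0.3 | 0.49 | 0.4813 | 11.1% |

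The rows with s = 1 are upper bounds for each m. With s = 0.25 the results are 4.1%, 5.1% and 6.3%.

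**4. Errors in the other direction.** Take the EEG component alone with a true share of 0.50, where P(go) = 0.5³ = 12.5%. If 30% of unchanged EEGs are called changed and 10% of changed EEGs are called unchanged, q = 0.50 × 0.70 + 0.50 × 0.10 = 0.40 and P(go) falls to 3.2%. An undefined call can therefore also work against C7.

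**5. Do comparable segments exist?** Sections 6.1 and 6.2.2 put admission at noon on Day 1, the first C7 dose on the morning of Day 2, the last dose that evening, and the end of EEG just before discharge at about noon on Day 3. The stretch from about noon on Day 1 to the first dose can therefore be matched by clock time to about noon on Day 2 until the same hour on Day 3. The hours between the first dose and noon on Day 2 have no clock-matched baseline.

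**The case against.** The strongest reply is that this is an exploratory pilot with an expressly unjustified sample size and mainly descriptive analysis, so coded scoring is a preference rather than the correction of an error. That would carry more weight if the plan only described the recordings. It does not: 9.1 ties a recommendation to proceed to the result.

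The definition might also sit elsewhere. Section 4.3.1 says that the earlier pilot established the feasibility of the EEG protocol, but no metric from it is carried into the outcome section. The front matter and the text between 9.3 and 9.5 were not available to me. Section 9.2 runs without a gap, and the text that resumes before 9.5 concerns membership of the monitoring committee.

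Several stronger readings are tempting, and the documents do not support them:

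- **That the EEG is read unmasked, or that masking was considered and rejected.** Open-label describes the treatment. On masking of the reading the plan is silent.
- **That a reader is already in place, so masked scoring needs no extra person.** No outcome reader is described. Section 5.3.3 mentions unit staff only for identifying and treating seizures.
- **That calls will drift toward unchanged.** This is plausible because no change is the hoped-for result, but step 4 shows that errors can run the other way.
- **That 27.1% is the expected false-go rate.** It is an upper bound at assumed inputs.

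The paired-test sentence in 9.5 is also weak evidence of a second EEG analysis in this trial, because its normal-diet wording does not fit a study confined to patients on the ketogenic diet. It still needs correcting.

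**Conclusion.** The concern holds in this form: the primary EEG outcome is promised a definition and receives none, the go rule cannot be applied to EEG as written, and no reader or masked reading is specified. These points rest on the text alone.

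The size is illustrative. If 40% of subjects are truly unaltered, groups are independent and 10% to 30% of changed EEGs are called unchanged, the chance of a false go rises from 3.2% to between 7.7% and 27.1% at most. It rises to between 5.1% and 11.1% if half of the altered subjects fail on EEG alone. The 40%, the misreading rates and the share failing on EEG alone are all assumptions, and neither the presence nor the direction of bias is shown. The gap should be closed before any recording is read for the outcome.

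**What to change.** In 9.2.1.1, before any recording is read for the outcome:

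1. **Name one metric**, for example epileptiform discharges per hour of artefact-free recording.
2. **Fix the windows**: about noon on Day 1 to the first C7 dose, against about noon on Day 2 to the same clock time on Day 3. State that the second window includes hours after the last dose.
3. **Set a numeric tolerance for unaltered.** Fix the number and length of segments, make the rule workable when the pre-C7 rate is zero, and say whether a decrease counts as a change. A limit set at the subject's own pre-C7 range would not do: with no baseline discharges, a single discharge would count as altered, and the limit would depend on how many segments are cut.
4. **Say who reads the EEG for the outcome**, and have that person score segments stripped of date, time and study day, coded and shuffled. Live safety monitoring stays unmasked.

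Use the same variable for the proportion and the paired test in 9.5, and correct the normal-diet wording there. Bring the synopsis and sections 3 and 9.1 into line, with an EEG-specific meaning of unaltered in 9.1.

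The cost is protocol wording and some technician time to cut and code segments for 15 subjects. No further recording or subjects are needed. Whether a further reader is needed cannot be judged, because the plan names none.

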9.2.1.2. Laboratory Assessments

C7 metabolism will not interfere with previously-acquired ketosis in G1D, as measured by no increase in observable seizure rate and no clinically relevant changes glycemia and ketosis, as measured by random glucose levels and beta-hydroxybutyrate levels, which will remain within the pre-enrollment clinically acceptable ranges (i.e., the new values will typically be within 2SD of previous values, using as SD the SD of the normal values as determined by the laboratory).

Subjects will experience no clinically relevant changes in observable seizures, random plasma glucose, or beta-hydroxybutyrate levels, as compared to the baseline values defined above.

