2. BACKGROUND

2.1. Rationale

Glucose transporter deficiency type 1 (G1D), a prototypic glycolytic defect that impairs the first step of glucose metabolism, was first described in 1991 and is caused by haploinsufficiency of the blood brain barrier and astrocyte glucose transporter (1-3). In its most common form, G1D leads to epilepsy and intellectual discapacity. Associated features include microcephaly (signifying limited brain growth) and movement incoordination (ataxia). There is no alteration of systemic carbohydrate metabolism.

Some manifestations of G1D are treatable in a significant fraction of patients: In ~2/3 of over 100 subjects that we have cared for over the years, a ketogenic diet has been efficacious for seizure control but without significantly impacting intellectual discapacity or ataxia ((4) and PI observations). Therefore, G1D is at least partially responsive to the alternative fuels generated by the diet in a fraction of patients, namely even-carbon-number fatty acids and ketone bodies (2). We currently care for over 100 G1D genetically-confirmed subjects, representing ~40% of all North American and ~10% of European subjects either reported or genotyped (often by us (5) under our NIH CETT Program for G1D) and we have elucidated the principal brain metabolic pathways in G1D (6). Although much work remains to be carried out to fully understand the biochemistry of the disorder, significant progress has been made in G1D, such that we believe that the finding of enhanced anaplerosis after administration of the C7 constituent heptanoate and related indicators of tricarboxylic acid (TCA) cycle stimulation (7) warrants the trial of anaplerotic therapy at this time in this disease. An additional sense of urgency is imposed by the potential window of opportunity that closes once the child brain matures.

Because heptanoate metabolism generates acetyl-CoA, C7 can potentially stimu-

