late hepatic neoglucogenesis and this can decrease ketosis via insulin release (113). Neoglucogenesis stemming from heptanoate was observed by us after infusion of heptanoate in G1D mice (28). However, the relative amount of heptanoate infused was far greater than that used for G1D subjects. This was expected because a large quantity of labeled substrate is necessary to achieve labeling of brain intermediary metabolites in human and mouse ^{13}C NMR experiments as developed by us (27, 32, 114, 115). Thus, no significant neoglucogenesis (i.e., an increase in glycemia >10 mg/dl) is obligatorily anticipated after C7 ingestion.

Preliminary studies. One G1D subject has received C7 at 45% while on a 3.5:1 ketogenic diet without clinical or analytical consequence. Our 14 G1D subjects on a regular diet studied in the fasting state (8) exhibited a mean blood glucose of 88.5 ± 1.9 mg/dl (mean \pm SEM), which did not significantly change 30-60 min after ingestion of the base dose (35%) of C7 (87.8 ± 2.4 mg/dl). Beta- hydroxybutyrate levels were also unchanged (0.25 ± 0.10 mM in the fasting state relative to 0.23 ± 0.1 mM in the post-C7 state; mean \pm SEM). The same conclusion was reached after 10 of these subjects were tested after 3 months on C7. Thus, C7 metabolism does not appreciably interfere with glucose metabolism and related ketosis (beta-hydroxybutyrate) under a regular diet.

Fifteen subjects with G1D (five per each of three age groups) and currently receiving a ketogenic diet will participate. After baseline measurements of common blood analytes, EEG, and blood ketone body levels, subjects will be given triheptanoin dosed by individual daily caloric intake, divided in 4 daily fractionated doses.

All subjects will take triheptanoin for 24 hours (4 doses) on an inpatient basis.

This study, if the hypothesis is correct, will enable future combined or comparative studies because, for 1/3 of G1D patients, the ketogenic diet is insufficient and may be supplemented with C7 or replaced by it depending on future work, whereas, conversely, C7 may prove insufficient as first line therapy in some patients and necessitate the addition of a ketogenic diet.

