6.2.2. On-Study/On-Intervention Evaluations

6.2.2.1. Entry Day 1

Subjects will be admitted for a 48 hour inpatient stay for oil administration and monitoring. Entry evaluations will be done within a day of pre-entry and consist of a nutritional assessment, and a blood draw to evaluate hematology and blood chemistry, including a random glucose. We will also obtain blood that is left over from the samples above (if available) or draw an additional 3 mL of blood, if needed, to measure C7 ketones. The collection of this blood for measurement of ketones is optional. A continuous EEG will be completed on subjects over the 48 hour inpatient stay. A peripheral IV will be placed to allow for immediate treatment of breakthrough seizures, should they occur.

6.2.2.2. Day 2

Subjects will be administered C7 starting on the morning of Day 2. Subjects will be given oil at a rate of 45% of their daily caloric intake, divided into 4 doses (breakfast, lunch, dinner, and before bed). A clinical assessment and a side effect assessment will be done. Subjects will be maintained on continuous EEG for the duration of C7 administration. Subjects will receive their final dose in the evening on Day 2. Subjects will have a blood draw to evaluate hematology and blood chemistry. Subjects will undergo a random glucose and beta-hydroxybutyrate level in the morning with their first dose of C7 and at bedtime with their last dose of oil. We will also obtain blood that is left over from the samples above (if available) or draw an additional 3 mL of blood, if needed, to measure C7 ketones. The collection of this blood for measurement of ketones is optional.

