6.3.3. Medical/Treatment History

Procedure location: Children's Medical Center Rare Brain Disorders Clinic. Facilitators: Principal Investigator or physician co-investigators. All subjects' symptoms, past medical history, and current and past treatments will be obtained using a standardized questionnaire that we have used extensively in metabolic encephalopathies to ensure that symptoms anticipated in G1D are sufficiently characterized (13, 14). For example, seizure frequency (the main indicator of neural dysfunction) is captured by this tool. However, in order to avoid ascertainment bias, a wide range of general questions related to all systems is included. This assessment takes approximately 30 minutes.

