6.3.8. Seizure count

Subjects and caregivers will be asked to count any seizures they note during the inpatient stay, from prior to oil administration to discharge on Day 3. They will be given a log to record time and description of any visible seizures.

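### About 20 h before C7 and 28 h after the first dose cannot support a claim of no increase in seizure rate; the claim should be narrowed to acute breakthrough seizures

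*Combined protocol and SAP*

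**What the plan says.** Sections 1.1 and 9.2.1.2 both set out the hypothesis that C7 does not disturb ketosis, "as measured by no increase in observable seizure rate". The synopsis lists change in seizure rate as a secondary outcome. Section 9.1 makes clinical seizure activity one of four things that must stay unaltered in at least 3 of 5 subjects in each age group before an efficacy trial is recommended.

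- **Window.** The schedule in 6.1 has admission at noon on Day 1 and discharge at noon on Day 3. Under 6.2.2, "Subjects will be administered C7 starting on the morning of Day 2", and 2.1 states "All subjects will take triheptanoin for 24 hours (4 doses) on an inpatient basis". In 6.3.8, subjects and caregivers "count any seizures they note during the inpatient stay, from prior to oil administration to discharge on Day 3".
- **Other counts.** A seizure count also appears among the Pre-Entry assessments (6.2.1.2) and at the Day 4 visit (6.2.3). Neither is given a role in the analysis.
- **Baseline.** The closing sentence of 9.2.1.2 reads: "Subjects will experience no clinically relevant changes in observable seizures, random plasma glucose, or beta-hydroxybutyrate levels, as compared to the baseline values defined above". The only range defined before it is a 2 SD range, "using as SD the SD of the normal values as determined by the laboratory". That can apply to glucose and beta-hydroxybutyrate but not to seizures.
- **History.** Section 6.3.3 says "seizure frequency (the main indicator of neural dysfunction) is captured by this tool". No section uses this frequency as the comparator.
- **Analysis.** Section 9.5 names no analysis of seizures.

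**The concern.** A rate is a count over time, and the time here is short against the spacing of seizures in many patients on the diet. With rare seizures, both windows will usually be empty and a real rise will go unseen. With daily seizures, the later window will often look worse than the earlier one by chance alone. No threshold or baseline is stated to separate the two cases.

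The component feeds a recommendation to proceed. A subject could be scored as altered with no change in risk, or as unaltered despite a doubled rate. A reader of a positive result could take the hypothesis on seizure rate as shown when about one day of exposure cannot show it.

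**Working it through.** The plan gives no figure to reproduce: no seizure rate, effect size or error rate is stated, and 9.3 says the sample size is not justified.

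**Inputs**
- Before C7: noon Day 1 to the morning of Day 2. A first dose at 08:00 (assumed) gives 20 h; at 06:00 it gives 18 h.
- After first dose: 08:00 Day 2 to noon Day 3, which is 28 h.
- Usual seizure rate λ per day: assumed, and varied.
- Rule: any higher rate after than before counts as an increase.

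**Formula.** Let X0 ~ Poisson(20λ/24) and X1 ~ Poisson(28rλ/24), where r = 1 is no effect and r = 2 is a doubling. An increase means X1/28 > X0/20, that is X1 > 1.4·X0. Then P(increase) = Σk P(X0 = k)·P(X1 > 1.4k).

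**One a week, λ = 1/7.** The means are 0.119 and 0.167.
- No effect: the k = 0 term is e^(−0.119)·(1 − e^(−0.167)) = 0.136, and k = 1 adds 0.001. The total is 0.138.
- Doubling: 0.252 + 0.005 = 0.256 with rounding, so it is missed in 0.744.

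**One a day, λ = 1.** The means are 0.833 and 1.167.
- No effect: 0.435·0.689 + 0.362·0.325 + 0.151·0.113 + a remainder below 0.001 = 0.434.
- Doubling: 0.392 + 0.245 + 0.062 + 0.004 = 0.704 with rounding, so it is missed in 0.296.

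| Usual rate | Increase shown, no effect | Doubling missed |
|---|---|---|
| 1/week | 14% | 74% |
| 3.5/week | 33% | 45% |
| 1/day | 43% | 30% |
| 2/day | 51% | 20% |
| 10/day | 50% | 3% |

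A tenfold rise from 1/week is seen in 77%.

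**Sensitivity.** With windows of 18/24, 20/28, 18/30 and 18/14 h, the false increase at 1/day or more is 38–51%, and a doubling at 1/week is missed in 73–85%. With overdispersed counts (negative binomial, k = 1), the false increase at 1/day or more is 32–50%.

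**Trial level, seizure component alone.** If a subject passes with probability p, a group passes with G = Σ(j=3..5) C(5,j)·p^j·(1−p)^(5−j), and all three groups pass with G³.
- *Every subject at the same rate, no effect:* at 1/day p = 0.566, G = 0.621, G³ = 0.24. At 2/day G³ = 0.12.
- *Every subject at 1/week, true doubling:* p = 0.744, G = 0.890, G³ = 0.70.
- *Two thirds seizure-free, one third at the stated rate:* p = 1 − P(increase)/3.

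| Rate in the other third | p, no effect | All three pass | p, doubling | All three pass |
|---|---|---|---|---|
| 1/week | 0.954 | 99.7% | 0.915 | 98% |
| 3.5/week | 0.892 | 97% | 0.817 | 87% |
| 1/day | 0.855 | 93% | 0.765 | 76% |
| 2/day | 0.831 | 89% | 0.733 | 68% |

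**A history-based limit instead.** Treat the 6.3.3 rate as known and flag the 28 h count only at the smallest c with P(X ≥ c) ≤ 0.05 (c = 2, 3, 4, 6 for the four rates).

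| Usual rate | False increase | Doubling detected | Detected by simple comparison |
|---|---|---|---|
| 1/week | 1% | 5% | 26% |
| 3.5/week | 2% | 11% | 55% |
| 1/day | 3% | 21% | 70% |
| 2/day | 3% | 33% | 80% |

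**The case against.** The strongest case against is that this is an exploratory study of an acute question. Section 7 names the worry as a rapid loss of ketosis leading to breakthrough seizures, and an inpatient day with continuous EEG fits that. Section 9.5 plans no seizure test. The go rule speaks of clinical seizure activity, not rate, and concludes compatibility. Section 9.2.1.2 also has the softer wording about clinically relevant changes. Read as at least a doubling (24 h on C7), that wording would bring false increases to about 30% at 1/day, 28% at 2/day, 9% at 10/day and 3% at 20/day.

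Much of this stands. The acute window is suitable for the acute question, and the go rule does not itself use the word rate. But the rate claim is in the hypothesis and the outcome, and the softer wording has no threshold.

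A reader might infer three stronger things that the documents do not support:
- **That the trial can see no seizure effect at all.** Large acute effects are visible, and at 10/day a doubling is missed in only 3%.
- **That the go decision is mostly chance.** That holds only if most subjects have frequent seizures. Section 2.1 says that in about two thirds of the patients cared for "a ketogenic diet has been efficacious for seizure control but without significantly impacting intellectual discapacity or ataxia". If that means seizure-free, the component passes in 89–99.7% of trials with no effect.
- **That the recorded history should become the pass/fail limit.** It lowers false increases but misses more doublings, treats a caregiver-reported frequency as known, and ignores clustering.

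**Conclusion.** The point holds in a limited form. The planned observation cannot support a statement that the seizure rate did not increase. With rare seizures a doubling is usually missed (74% at 1/week), and with daily seizures an unaffected subject fails a strict reading nearly half the time (43% at 1/day, about 50% at 2/day or more). What the trial can show is whether an acute excess of seizures appears in about 28 h.

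For the trial decision, the direction depends on the case mix. With two thirds seizure-free the problem is mainly insensitivity: the component still passes in all three groups in 68–98% of trials when the remaining third has a doubled rate of seizures. If nearly all subjects had daily seizures, chance failure would dominate.

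Every percentage rests on an assumed seizure rate, Poisson counts, a first dose at about 08:00 and the any-rise rule. Reading two thirds as seizure-free is also an assumption, since the protocol says only that the diet was efficacious. Seizure rate is secondary in the synopsis, but its place in the go rule makes the wording worth correcting.

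**What to change.** In 1.1, 9.1 and 9.2.1.2:
1. Replace the seizure-rate claim with: *no excess of acute breakthrough seizures in the roughly 28 h from first C7 dose to discharge*.
2. State that a change in seizure rate is not assessed.
3. Report each subject's pre-dose and post-dose counts, with the hours observed, beside the usual seizure frequency from 6.3.3.
4. If a history-based Poisson limit is shown, label it supportive description and do not use it as the pass/fail rule.

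The investigators should also write down before enrolment how an acute breakthrough seizure is judged in a subject with residual seizures, and what role, if any, the Pre-Entry and Day 4 counts have.

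The cost is wording and one listing from data already collected. No visit, subject or procedure is added, and seizure care on the unit is untouched. The downside is a narrower stated conclusion about seizures.
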